#### **5.4.2 Contraception**

The effects of INCB039110 on the developing human fetus are unknown. For this reason and because JAK inhibitor agents are known to be teratogenic, women of childbearing potential and men with partners of childbearing potential must agree to use highly effective contraception from the start of study therapy, for the duration of study therapy, and for 30 days after the last dose of INCB039110. Should a woman become pregnant or suspect she is pregnant while she or her partner is participating in this study, she should inform the treating investigator immediately. Men treated or enrolled on this protocol must also agree to the use of highly effective contraception prior to the study, for the duration of study participation, and 30 days after completion of INCB039110 administration.

Acceptable highly effective contraceptive methods include:

- Bilateral tubal occlusion
- Vasectomized partner
- Intra-uterine device (IUD) or hormone-releasing system (IUS)
- Any hormonal (estrogen combined with progesterone or progesterone alone) contraception associated with inhibition of ovulation: implanted, oral, intravaginal, transdermal, or injectable.
- The combination of two compatible barrier methods with or without spermicide (i.e., diaphragm, sponge, or male or female condoms).
- Abstinence from heterosexual intercourse.

## **6 TREATMENT PLAN**

### **6.1 Administration Schedule**

Treatment will be administered on an outpatient basis. Eligible patients will self-administer itacitinib every morning regardless of food. At the end of 8 weeks of combination therapy, patients will start a standard ECP taper schedule and itacitinib will be continued at the assigned dose level. Patients achieving PR or better after 6 cycles of itacitinib may continue treatment with itacitinib for up to 1 year. Thereafter, itacitinib may be tapered at the treating investigator's discretion as described below.

### 6.1.1 ECP Taper

ECP will be given at a frequency of twice weekly for 8 weeks followed by a standard taper schedule as detailed below. Local institutional guidelines should be followed for the safe administration of ECP. Once a taper has initiated, investigators may consider increasing the frequency of ECP by one level if there is concern for GVHD progression and if prednisone (or prednisone equivalent) is not administered. This should be discussed with the PI first.

**Table 4: Recommended ECP Schedule**

Week	ECP Schedule
1-8 (Start of therapy)	Twice weekly
9-16	Once weekly
17-24	Once every other week
25+ until physician discretion	Once monthly

During the taper, immune suppression will continue as described below.

### 6.1.2 Itacitinib Taper

If a participant has achieved CR or PR after six cycles of therapy, investigators may continue itacitinib for up to 1 year. Thereafter, investigators may begin to taper the dose of itacitinib by 1 dose level. Subsequent tapering may occur within 28 to 56 days after the initial taper, as appropriate. Participants who are still receiving CNIs, sirolimus, or corticosteroids for GVHD treatment at this time may continue to do so at the treating investigator's discretion. If GVHD signs/symptoms worsen during the taper of itacitinib, the dose may be escalated by 1 dose level.

### 6.1.3 Prednisone Taper

If a participant has been initiated on prednisone dose (or its equivalent) during treatment with ECP and Itacitinib, investigators may begin to taper the corticosteroid dose as per their institutional guidelines or at the treating investigator's discretion. Participant's prednisone dose (or its equivalent) should be at < 0.25mg/kg/d after 8 weeks from initiation of corticosteroid. If this is not achieved, the participant will be considered a treatment failure but may remain on study treatment and follow-up period.

### 6.1.4 Immune Suppression with Calcineurin Inhibitors or Sirolimus

Tapering of standard immune suppression (tacrolimus, cyclosporin, sirolimus) used for prophylaxis or treatment of acute GVHD may be tapered at the physician's discretion. If immune suppression is at treatment doses for cGVHD, tapering of immune suppression should only occur after the subject has achieved a treatment response and after following the withdrawal of prednisone (if applicable).

CNIs and/or sirolimus may be reduced per institutional practices.

## **6.2 Itacitinib**

### **6.2.1 How Supplied, Stored, Packaged and Labeled**

Incyte will supply itacitinib as 100 mg sustained-release tablets. These tablets contain the active ingredients, microcrystalline cellulose, lactose monohydrate, pregelatinized starch, hydroxypropyl cellulose, sodium starch glycolate, and magnesium stearate.

Investigationally labeled bottles will be packaged in high-density polyethylene bottles with child-resistant closures including an induction seal liner. They will be dispensed by appropriately trained and delegated personnel to patients. If dose modifications are necessary, patients will be dispensed the appropriate number of investigationally labeled bottles.

Store at ambient conditions 15°C to 30°C (59°F to 86°F). Protect from moisture and light. Do not place the medication in pillboxes.

### **6.2.2 Preparation and Administration**

Investigational study medication will be prepared and dispensed by properly trained and delegated individuals. Patients will self-administer itacitinib by mouth regardless of food once daily. Doses should be taken every morning ( $\pm$  8 hours) and recorded on the patient's dosing diary. Patients should be instructed to hold their dose until after their blood is drawn on days that they will be seen in the clinic. Doses missed outside of the dosing window should not be made up, but rather, patients should be instructed to take their next dose at their regularly scheduled time.

### **6.2.3 Accountability and Compliance**

A patient dosing diary will be provided to the patients to aid in patient compliance with the dosing instructions. The diary will be maintained by the patient to include missed or changed itacitinib doses. The time of each dose administration and the number of tablets taken each day will be recorded in the dosing diary. Patients will be required to return the completed patient dosing diary on Day 1 of every cycle for timely review by site personnel and discussion of missed doses and/or compliance issues.

Patients will also be required to return all unused itacitinib tablets at the end of every cycle. The number of tablets returned by the patient will be counted, documented, and recorded by site personnel and reconciled with the patient's dosing diary to support the itacitinib accountability process. Excess or unused study drug returned to the investigative site will be destroyed in accordance with GCP after drug accountability has been performed.

Treatment compliance (reported as a percent) will be defined as the number of tablets or capsules taken during the study divided by the expected number of tablets or capsules, multiplied by 100%.

### **6.3 Extracorporeal Photopheresis**

All ECP treatments will be prepared and administered according to local institutional practices and guidelines. All doses will be administered at the investigational site by well-trained medical staff. The start and stop times of the infusions, along with the total volume administered, will be recorded in the patients' medical records. Additionally, the start and stop times of any interruptions to infusions and/or changes in the rate of infusion will also need to be recorded in the patients' medical records. Any reason that treatment is missed or altered should be clearly documented in the patient's research chart.

Due to the risk of thromboembolic events, clinic staff involved in ECP procedures will be advised to be alert for symptoms of pulmonary embolism (PE) and deep vein thromboembolism (DVT) during and following ECP therapy. Symptoms may include shortness of breath, cough, chest pain, fever, cyanosis, leg pain with or without swelling, dizziness, and irregular heartbeat. Patients will be advised upon discharge that should they develop these symptoms to immediately seek urgent medical attention at the nearest emergency room. Treating investigators should consider the necessity of anticoagulation and heparin dose adjustment according to device labeling and individual patient need.

### **6.4 Concomitant Medications and Therapies**

All concomitant medications and treatments utilized 28 days prior to Cycle 1 Day 1 and 30 days after the last dose of study medication must be recorded in the patient's Case Report Form (CRF). The subject needs to notify the investigational site about any new medications he/she takes after the start of the study drug. All medications (other than study drug) and significant nondrug therapies (including physical therapy and blood transfusions) administered after the subject starts treatment with study drug must be listed on the Concomitant Medications/Significant Nondrug Therapies after the start of the study drug.

Since there is a potential for interaction of itacitinib with other concomitantly administered drugs through the cytochrome P450 system, the case report form must capture the concurrent use of all other drugs, over-the-counter medications, or alternative therapies. The Principal Investigator should be alerted if the patient is taking any agent known to affect or with the potential for drug interactions. The study team should check a frequently updated medical reference for a list of drugs to avoid or minimize the use of.

### **6.5 Ancillary Therapy and Supportive Care**

Topical corticosteroid therapy and regimens to treat or prevent bronchiolitis obliterans (e.g., inhaled corticosteroids) may be continued per institutional guidelines.

Other supportive medications in accordance with standard clinical practice (such as for emesis, diarrhea, osteoporosis etc.) are permitted. Use of neutrophil growth factors (filgrastim and pegfilgrastim), red blood cell growth factors (erythropoietin) or TPO receptor agonists (romiplostim, eltrombopag) is permitted per institutional policy for Part 2 participants only. Transfusions may be given in accordance with institutional policy.

## **6.6 Prophylaxis for Infectious Diseases**

### **6.6.1 Pneumocystis Pneumonia Prophylaxis**

All subjects receiving study treatment with INCB039110 are required to receive a standard PJP prophylaxis regimen determined by the investigator. Examples of standard PJP prophylaxis therapies for this population include trimethoprim-sulfamethoxazole, atovaquone, dapsone with or without pyrimethamine, and pentamidine (NCCN 2014). Subjects with a previous or suspected allergy to sulfonamide antibiotics must receive prophylaxis with atovaquone (Mepron) or pentamidine. Prophylaxis should be given while subjects are receiving study treatment and continue at a minimum an additional 60 days after the last dose of itacitinib or through the taper of all immunosuppression.

### **6.6.2 Prophylaxis for Encapsulated Bacteria and Fungal Infections**

Antibiotic and antifungal prophylaxis should be given per institutional standards while subjects are receiving study treatment. Concomitant use of strong CYP3A4 inhibitors such as itraconazole, voriconazole, and clarithromycin are restricted during study therapy. If antifungal therapy is necessary, use of an agent with less CYP3A4 inhibition is recommended, such as posaconazole, isavuconazole, or fluconazole. Careful monitoring of hematology parameters and clinical signs and symptoms of itacitinib-related adverse reactions is recommended upon initiation of a CYP3A4 inhibitor.

### **6.6.3 Restricted Therapy**

The following medications have restrictions on use during the treatment period of the study.

- Use of potent CYP3A4 inhibitors, such as itraconazole, voriconazole, mibefradil, and clarithromycin. If treatment with one of these drugs is required, a dose reduction of itacitinib to 100 mg daily is recommended.
  - Based on the low overall bioavailability of topical ketoconazole, there are no restrictions on topical ketoconazole in the study.
  - No dose adjustment is recommended for concomitant administration of other CYP3A4 inhibitors.
- P-glycoprotein substrates of clinical relevance should be used with caution.
- If concomitant administration of an anticoagulant/antiplatelet medication is indicated, then caution and enhanced monitoring are required. The presence and severity of thrombocytopenia should be a factor in the choice of anticoagulant and dose. The use of aspirin at doses > 81 mg per day should be avoided. Acetaminophen and nonsteroidal anti-inflammatory agents (NSAIDs, e.g., ibuprofen) may be used at over-the-counter doses. Due to the risk of liver injury with the use of high doses of acetaminophen, subjects should be advised to stay within the recommended daily dose of acetaminophen.

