## 2.3 Justification for Dose

In a Phase 1 study (INCB 39110-108) that assessed the safety and tolerability of itacitinib in combination with corticosteroids, 30 acute GVHD participants were randomized to 1 of 2 treatment cohorts (200 mg cohort, n = 14; 300 mg cohort, n = 16). The Day 28 ORR in first-line acute GVHD participants in both treatment cohorts was 83.3%; for participants with steroid-refractory acute GVHD, the ORR at Day 28 was 64.7% (200 mg cohort, 62.5%; 300 mg cohort, 66.7%). One DLT of Grade 3 thrombocytopenia was reported in 1 participant with pre-existing thrombocytopenia who was randomized to the 300 mg cohort. Adverse events reported in greater than 20% of all participants include diarrhea, hypokalemia, peripheral edema, hyperglycemia, abdominal pain, hypophosphatemia, fatigue, headache, hypomagnesemia, and sepsis. Thrombocytopenia and platelet count decreased were observed in 24.2% and 20.7% of participants, respectively, with a higher proportion of these events occurring in the 300 mg cohort, although a higher incidence of pre-existing

thrombocytopenia was also observed in this group. Among both dose groups (200 mg and 300mg daily), itacitinib was generally well-tolerated with an AE profile as expected.

Mild decreases in platelet count of 5000-10,000/mcl is expected to occur following a scheduled ECP session. As itacitinib 300 mg daily has been reported to have a higher incidence of thrombocytopenia/platelet decrease as compared to itacitinib 200 mg daily, we will test the combination of ECP with itacitinib 200 mg daily.

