### **Dose Modifications for Concomitant Medications**

Observed data from Study INCB 39110-108 suggest that there is an approximately 2-fold increase in exposure when itacitinib is co-administered with a potent CYP3A4 inhibitor. In a healthy volunteer study, co-administration of itacitinib 200 mg with itraconazole 200 mg QD resulted in a nearly 5-fold increase in exposure. This discrepancy may be due to the fact that at the time of steady-state PK determination, all of the participants in INCB 39110-108 except 1 were on posaconazole, a less potent inhibitor than itraconazole based on midazolam fold change. A PBPK model was used to simulate an itacitinib 100 mg QD dose when co-administered with itraconazole. The resulting exposure (2306 nM·h) approximates that observed in GVHD patients taking 300 mg QD alone (2855 nM·h). Therefore, it is recommended that participants do not take the following potent CYP3A4 inhibitors while on itacitinib: itraconazole, voriconazole, mibefradil, and clarithromycin. No dose modification is recommended for concomitant administration of CYP3A4 inhibitors less potent than itraconazole, for example, posaconazole. The solubility of itacitinib is > 1.10 mg/mL (and therefore > 200 mg/250 mL or 300 mg/250 mL) at pH values up to 4.3. In most cases of treatment with gastric acid-reducing agents, the target pH is approximately 4, and in those situations, there should not be any significant impact on the absorption of itacitinib. The lack of impact of gastric pH-modifying agents was supported through graphical analysis and modeling of observed data along with PBPK model. No dose modification of itacitinib is recommended in participants concomitantly taking gastric pH modifying agents.

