### 3.1.2 Nonclinical Drug Metabolism and Pharmacokinetics

In single-dose PK studies in rats, dogs, and monkeys, orally administered itacitinib was rapidly absorbed ( $t_{max} \leq 2.0$  hours). The protein binding of itacitinib in plasma and serum from rats, dogs, and humans was moderate (unbound fraction of 29%-43%) and not dependent on itacitinib concentration.

Itacitinib has minimal penetration across the blood-brain barrier in rats. Protein binding in plasma and serum from rats, dogs, and humans was moderate, and the fraction unbound was independent of itacitinib concentration. In rats and dogs, excretion was rapid and complete after a single oral dose of 14C-INCB039110.

The major analyte present in plasma and urine from all species studies was parent compound. CYP3A4 is the major isozyme responsible for the metabolisms of itacitinib. Itacitinib did not inhibit or induce CYP activity, suggesting a low potential for drug-drug interactions.

Preliminary PK analysis showed that following multiple-dose administration of itacitinib SR formulation, itacitinib attained peak plasma concentrations with a median  $t_{max}$  of 1.89 hours to 3.78 hours. For increasing dose regimens between 100 mg BID and 200 mg BID, itacitinib plasma exposures ( $C_{max}$  and AUC) appeared to be dose-proportional. The itacitinib AUC for 600 mg QD in subjects with PMF, PPV-MF, and PET-MF was comparable to that of 600 mg QD in subjects with stable, chronic plaque psoriasis.

Additional information on pharmacology, drug disposition, and nonclinical toxicology is available in the itacitinib IBv10.

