#### 4.2 Part 1: Dose De-Escalation

A total of 6 to 18 patients may be evaluated in Part 1 depending on the frequency of DLTs and the need for dose reductions. A 3+3 dose de-escalation design will be used to determine the recommended phase two dose while ensuring the safety and tolerability of the treatment. In this trial, the dose determined to be the maximum tolerated dose will be the recommended phase two dose and will be utilized in the cohort expansion. The study may test the possibility of three dose levels of itacitinib as described in Table 1.

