**Table 5: Itacitinib Dose Levels**

Dose Level	Itacitinib
1	200 mg oral daily, Days 1-28 each cycle
-1	100 mg oral daily, Days 1-28 each cycle
-2	100 mg oral every other day, Days 1-28 each cycle

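### The fixed 100 mg dose for use with a potent CYP3A4 inhibitor reduces nothing at level -1, gives no usable instruction at level -2, and leaves level -1 patients evaluable for DLT at raised exposure

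*Combined protocol and SAP*

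**What the plan says.** Section 6.6.3 restricts potent CYP3A4 inhibitors (itraconazole, voriconazole, mibefradil and clarithromycin are named). If one is needed, "a dose reduction of itacitinib to 100 mg daily is recommended". Other CYP3A4 inhibitors need no adjustment.

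Table 5 defines three itacitinib levels: 200 mg daily (level 1), "100 mg oral daily, Days 1-28 each cycle" (level -1), and 100 mg every other day (level -2). Patients reach the lower levels by Part 1 de-escalation (Section 4.2), by reduction for toxicity (Section 7.3, Table 6) or by taper (Section 6.1.2). Level -1 can also become the study dose, because under Section 4.2 "the dose determined to be the maximum tolerated dose will be the recommended phase two dose and will be utilized in the cohort expansion".

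The pharmacology is in Section 2.3. In healthy volunteers, "co-administration of itacitinib 200 mg with itraconazole 200 mg QD resulted in a nearly 5-fold increase in exposure". In patients, nearly all on posaconazole, the rise was about 2-fold. A PBPK simulation of 100 mg daily with itraconazole gave 2306 nM·h, which "approximates that observed in GVHD patients taking 300 mg QD alone (2855 nM·h"). The same section explains the starting dose: "As itacitinib 300 mg daily has been reported to have a higher incidence of thrombocytopenia/platelet decrease", 200 mg was chosen for use with ECP.

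Section 7.1 says that a reduction made for a drug interaction is not a DLT and that the patient is non-evaluable and replaced. Section 12.3 likewise replaces participants whose dose was reduced because of a concomitant medication.

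**The concern.** A rule written as a dose reduction should reduce the dose at every level where it can be used. This one does so only at level 1. The patients it misses include those for whom 200 mg with ECP was already too much. For them, following the rule exactly can cancel the lower dose.

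There is a second effect in Part 1. At level 1, a patient who starts itraconazole in the DLT period is reduced and therefore replaced. At level -1 the same event causes no reduction, so the replacement rule is not triggered. A DLT at raised exposure could then count towards the limit of 1 in 6. The error leans towards over-counting DLTs. That is cautious for safety, but it could wrongly reject level -1.

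**Working it through.** **Step 1: the rule at each level** (Section 6.6.3 against Table 5)

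| Level | Mean daily dose | Dose under the rule | Change |
|---|---|---|---|
| 1 | 200 mg | 100 mg | -50% |
| -1 | 100 mg | 100 mg | 0% |
| -2 | 50 mg | 100 mg if read literally | not a reduction, so no usable instruction |

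**Step 2: the plan's own comparison.** 2306/2855 = 0.81, so 100 mg with itraconazole is simulated at about four-fifths of the exposure seen at 300 mg alone. The PBPK output cannot be re-derived from the documents.

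**Step 3: exposure without an inhibitor.** This assumes dose proportionality down from 300 mg daily.
- 200 mg daily: 2855 x 2/3 = 1903 nM·h
- 100 mg daily: 2855/3 = 952 nM·h

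Support for proportionality is limited: "For increasing dose regimens between 100 mg BID and 200 mg BID", exposure appeared dose-proportional (Section 3.1.2). Nothing is given for once-daily or every-other-day dosing in this range.

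**Step 4: level -1 with an inhibitor, dose unchanged.** The fold change is assumed to be the same at 100 mg as at 200 mg.

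| Interaction figure | Exposure (nM·h) | Relative to 200 mg alone |
|---|---|---|
| 2-fold (mostly posaconazole) | 952 x 2 = 1903 | 1.0 |
| PBPK value | 2306 | 2306/1903 = 1.2 |
| 5-fold (itraconazole, volunteers) | 952 x 5 = 4758 | 2.5 |

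The first row is a floor. It comes mainly from a drug that the plan treats as needing no adjustment. The middle row sets a simulated value against scaled patient data. If the model carried the near 5-fold interaction, its own 100 mg baseline would be about 2306/5 = 461, not 952. The 1.2 is therefore indicative only.

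**Step 5: one Table 5 level lower.** Going from 100 mg daily to 100 mg every other day is assumed to halve mean daily exposure.

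| Interaction figure | Mean daily exposure (nM·h) | Relative to 200 mg alone |
|---|---|---|
| 2-fold | 952 | 0.5 |
| PBPK value | 2306/2 = 1153 | 0.6 |
| 5-fold | 4758/2 = 2379 | 1.25 |

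Every ratio in Step 4 is halved, but the 5-fold case stays above the 200 mg exposure. The dose taken on each dosing day is also unchanged.

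**Step 6: evaluability in Part 1.** Section 12.2.1 asks for at least 60% of planned doses, or a DLT. A level -1 patient on itraconazole who keeps taking 100 mg daily meets this. Sections 7.1 and 12.3 act only on a dose reduction, and none has occurred. Table 3 exempts an event clearly associated with a concomitant medication, but only among Grade 3 non-hematologic toxicities. Hematologic and Grade 4 events are not exempt.

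**Step 7: the efficacy design.** With p the true response rate, the probability of rejecting the null is the sum over x = 8 to 16 of P(X1 = x) x P(X2 >= 24 - x), where X1 ~ Bin(16, p) and X2 ~ Bin(30, p). This gives 0.0486 at p = 0.40 and 0.8006 at p = 0.60, matching Section 12.1. The dosing gap does not enter this calculation.

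**The case against.** The best defence is that 100 mg daily is an exposure ceiling and not a step down. Section 2.3 compares it with 300 mg alone, and 2306 is below 2855. Both 200 mg and 300 mg are described there as generally well tolerated. That reading is reasonable for patients who tolerate 200 mg. It does not serve those at level -1 because they did not, and it leaves level -2 without an instruction. The tolerability data are also from use without ECP.

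The case should be uncommon, too. Section 2.3 advises against these drugs, and Section 6.6.2 names alternatives and asks for monitoring when an inhibitor is started. In Section 6.4, "The Principal Investigator should be alerted if the patient is taking any agent known to affect or with the potential for drug interactions". Section 7.4 leaves room for clinical judgment, and Table 6 handles toxicity after the DLT period. Section 16.3 has the medical monitor told of each DLT. All of this lowers the likelihood and the consequences. None of it gives a dose for level -1 or -2, and the one-level step in Section 7.3 is written for toxicity.

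A reader might infer more than the documents support:
- **That the trial's error rates or sample size are compromised.** They are not (Step 7).
- **That every DLT during inhibitor use at level -1 would be miscounted.** The Table 3 exemption removes some.
- **That Section 6.6.3 tells level -2 patients to double their dose.** It speaks of a reduction, so it simply does not address them.
- **That one level down restores the intended exposure, or that the plan has accepted a 1.2 ratio at level 1.** The plan's benchmark is 300 mg alone, and the 5-fold case stays above the 200 mg exposure.

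**Conclusion.** The gap is real and can be read directly from the text: no reduction at level -1, no usable instruction at level -2, and a Part 1 replacement rule that is not triggered at level -1. If the rule is followed, a patient who failed 200 mg could return to about 1.0 to 2.5 times the 200 mg exposure. That range assumes dose proportionality and an equal fold change at 100 mg, and its middle value mixes simulated with observed data. The number of patients affected is not given and should be small. This is a dosing, safety and DLT-evaluability matter that merits an amendment. It does not threaten the efficacy test.

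**What to change.** **Section 6.6.3.** Replace the fixed target with a reduction of one Table 5 level while the inhibitor is given: 200 mg daily to 100 mg daily, and 100 mg daily to 100 mg every other day. At level -2, avoid the inhibitor or interrupt itacitinib after discussion with the Principal Investigator. Allow return to the prior dose once the inhibitor stops.

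**Section 7.3.** State that the ban on re-escalation does not apply to interaction-driven reductions. Otherwise a short course of clarithromycin could fix a level -1 patient at 100 mg every other day.

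**Sections 7.1 and 12.3.** Base non-evaluability and replacement on use of a potent CYP3A4 inhibitor in the DLT period, not on a dose reduction having occurred. A DLT that starts before the inhibitor still counts. No separate adjudication step is needed, and no exemption from the noncompliance rule in Section 6.7.1.

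**Cost.** Amendment wording in four sections. The existing 100 mg tablets suffice, and planned visits and evaluable numbers do not change. Part 1 may need an extra replacement, with a DLT period of about 7 + 28 = 35 days. Patients receive less itacitinib (or none, if interrupted at level -2) during inhibitor use. Because the lower step does not fully offset a 5-fold interaction, the advice against these inhibitors and the monitoring in Section 6.6.2 must stay.
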